8.5.2 Restricted drugs

(1) Iron supplements

From the first day of the screening period to completion of blood sampling for haematology tests on the final day of the treatment period, administer iron supplements to maintain serum ferritin values of ≥ 100 ng/mL or TSAT of $\geq 20\%$. Iron supplements may be omitted for subjects who respond poorly to them, such as those with an allergy or those with adverse drug reaction (ADRs) to iron (vomiting, etc.).

Investigators/subinvestigators will determine iron supplement dosage and administration route.

Important: Oral iron supplements may impair MT-6548 bioavailability, so oral iron supplements must not be taken at the same time as MT-6548 Tablet. Subjects taking oral iron supplements will be instructed not to take any within 2 hours before or after taking MT-6548 Tablet.

(2) Iron-containing phosphate binders (ferric citrate hydrate, sucroferric oxyhydroxide)

New use of iron-containing phosphate binders is fundamentally prohibited from the first day of the screening period to completion of blood sampling for haematology tests on the final day of the treatment period. If iron-containing phosphate binders are used by a subject on the first day of the screening period, then the same dosage of the same type should fundamentally be continued from the first day of the screening period to completion of blood sampling for haematology tests on the final day of the treatment period. If investigators/subinvestigators determine that a dosage increase is required for iron-containing phosphate binders, then additional treatment will be performed with hyperphosphatemia drugs containing no iron, or treatment switched to hyperphosphatemia drugs containing no iron. Dosage of iron-containing phosphate binders may also be reduced if determined necessary according to the subject's condition. For subjects in the correction cohort, there must be no switching to other hyperphosphatemia drugs containing no iron from the first day of the screening period to completion of scheduled tests at Week 4 of the treatment period.

Important: As with oral iron supplements, iron-containing phosphate binders may impair MT-6548 bioavailability, so iron-containing phosphate binders must not be taken at the same time as MT-6548 Tablet. Subjects taking iron-containing phosphate binders will be instructed not to take any within 2 hours before or after taking MT-6548 Tablet.

Rationale

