10.1.3 Other endpoints

The following endpoints will also be studied.

- (1) Correction cohort only: Change from baseline in mean Hb of Weeks 20 and 24, and Weeks 48 and 52, of treatment period.

Change from baseline in mean Hb of Weeks 20 and 24, and Weeks 48 and 52 of treatment period, will be calculated.

- (2) Correction cohort only: Ratio of subjects with an increase of ≥ 1.0 g/dL of mean Hb from baseline at each timepoint in treatment period.

Ratio of subjects with an increase of ≥ 1.0 g/dL of mean Hb from baseline at each timepoint in treatment period will be calculated.

- (3) Ratio of subjects who received ESA rescue therapy

Ratio of subjects who received ESA rescue therapy from the first day of the treatment period to treatment period Weeks 24 and 52 will be calculated.

- (4) Ratio of subjects who received red blood cell (RBC) transfusion rescue therapy.

Ratio of subjects who received RBC transfusion from the first day of the treatment period to treatment period Weeks 24 and 52 will be calculated.

- (5) Study drug dosage

MT-6548 Tablet: Mean daily dosage will be calculated for each scheduled study visit from the first day of the treatment period up to treatment period Week 52.

Darbepoetin alfa injection: Mean weekly dosage will be calculated for each scheduled study visit from the first day of the treatment period up to treatment period Week 52.

- (6) MT-6548 group only: total number of dosage adjustments

The total number of dosage adjustments from the first day of the treatment period to treatment period Weeks 24 and 52 will be calculated.

- (7) Quantity of iron administered

Mean weekly dosage will be calculated for each scheduled study visit from the first day of the treatment period up to treatment period Week 52.

- (8) Ratio of subjects who received IV iron

Ratio of subjects who received IV iron from the first day of the treatment period to treatment

period Weeks 24 and 52 will be calculated.

(9) Ratio of subjects with serum ferritin of ≥ 100 ng/mL or TSAT $\geq 20\%$.

Ratio of subjects with serum ferritin of ≥ 100 ng/mL or TSAT $\geq 20\%$ at each evaluation timepoint will be calculated.

(10) Change from baseline of iron-related measures (serum iron, TIBC, TSAT, and serum ferritin) and hepcidin.

Changes in iron-related measures (serum iron, TIBC, TSAT, and serum ferritin) and hepcidin from baseline will be calculated for each evaluation timepoint.

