Descriptive statistics of the change in the mean dose of iron supplement per month from the baseline (mean dose of iron during the screening period) should be calculated, after the first day of the treatment

period, in each period between scheduled study visits and during the entire treatment period from the first day to Week 52 of the treatment period. Before and after comparison should be conducted for changes from baseline using the paired t-test. The changes should be compared between groups using the Student-t test. The mean value of the between-group difference (MT-6548 – darbepoetin), its two-sided 95% CI, t-statistic, and p-value should be provided.

The dosage of iron supplement should be calculated using the dose as iron.

If no iron supplement is administered, the dose should be tabulated as 0 mg. Subjects who changed the administration route of an iron supplement during the treatment period and subjects who had never received an iron supplement during the treatment period should be excluded from the tabulation.

(8) Proportion of subjects receiving oral, intravenous, or (any route) administration of iron supplements

The number and proportion of subjects and the 95% CI (Clopper-Pearson [Exact] method) for the proportion of subjects treated with oral, intravenous, or oral iron supplement (any route) should be provided by treatment group for screening period, and after the first day of the treatment period, in each period between scheduled study visits and during the entire treatment period from the first day to Week 52 of the treatment period. McNemar tests should be used to compare baseline values (proportion of subjects receiving iron supplements by the aforementioned route in the screening period) with those before and after each period between scheduled study visits. The estimate, its 95% CI (exact method), and p-value (Fisher's exact test) for between-group difference (MT-6548 – darbepoetin) should be calculated for the proportion of subjects receiving oral, intravenous, or (any route) iron supplement.

Subjects who have not received an iron supplement are to be subjects who have never received an iron supplement during the relevant period, and subjects who have received an oral, intravenous, or (any route) iron supplement are to be subjects who have received an iron supplement at least once during the relevant period.

(9) Proportion of subjects with serum ferritin values of ≥ 100 ng/mL or TSAT of $\geq 20\%$.

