4.12 Iron supplement dosage

The dose of iron supplements is defined by the following formula. However, the dose of iron supplements will not be calculated if iron supplements are used as needed.

Mean monthly dose of iron supplements during the screening period* and each scheduled study visit period** (tabulation period of iron supplements) = (Daily dose based on the physician's prescription \times Period of administration (days) of the corresponding dose*** during the tabulation period of iron supplements)/Tabulation period of iron supplements (days)**** \times 30.4375****

*: The number of days of the screening period is “First day of the treatment period – First day of the screening period”.

**: For each period between the scheduled study visits, the actual study visit dates are not considered, and this tabulation is fixed as follows:

- ✓ The first day of the treatment period to Week 2 of the treatment period: The first day of the treatment period (1 day) to 14 days
- ✓ Week 2 of the treatment period to Week 4 of the treatment period: 15 to 28 days
- ✓ The same shall apply thereafter, and the final period between the scheduled study visits should be Week 20 to Week 24 of the treatment period: 141 days to a blood sampling day for hematological tests at Week 24 of the treatment period. However, for subjects who discontinued their treatment, the final period between the scheduled study visits should be up to the day before discontinuation.

***: If there are multiple applicable doses, the sum of the calculated values for each dose should be used.

****: For subjects who discontinued their treatment, the final period between the scheduled study visits (days) should be the actual number of days until the day before discontinuation.

*****: In this tabulation, 1 month month is counted as 30.4375 days (365.25/12 = 30.4375).

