Descriptive statistics of the change in the mean dose of iron supplement per month from the baseline (mean dose of iron during the screening period) should be calculated, after the first day of the treatment period, in each period between scheduled study visits and during the entire treatment period from the first day to Week 24 of the treatment period. Before and after comparison should be conducted for changes from baseline using the paired t-test. The changes should be compared between groups using the Student-t test. The mean value of the between-group difference (MT-6548 – darbepoetin), its two-sided 95% confidence interval, t-statistic, and p-value should be provided.

The dosage of iron supplement should be calculated using the dose as iron.

Confidential

If no iron supplement is administered, the dose should be tabulated as 0 mg. Subjects who changed the administration route of an iron supplement during the treatment period and subjects who had never received an iron supplement during the treatment period should be excluded from the tabulation.

(8) Proportion of subjects receiving oral, intravenous, or (any route) administration of iron supplements

The number and proportion of subjects and the 95% confidence interval (Clopper-Pearson [Exact] method) for the proportion of subjects treated with oral, intravenous, or oral iron supplement (any route) should be provided by treatment group for screening period, and after the first day of the treatment period, in each period between scheduled study visits and during the entire treatment period from the first day to Week 24 of the treatment period. A McNemar test should be used for before and after comparison between baseline (ratio of subjects receiving iron supplements by the aforementioned route in screening period) and each period between scheduled study visits. The estimate, its 95% CI (exact method), and p-value (Fisher's exact test) for between-group difference (MT-6548 – darbepoetin) should be calculated for the proportion of subjects receiving oral, intravenous, or (any route) iron supplement.

Subjects who have not received an iron supplement are to be subjects who have never received an iron supplement during the relevant period, and subjects who have received an oral, intravenous, or (any route) iron supplement are to be subjects who have received an iron supplement at least once during the relevant period.

(9) Proportion of subjects with serum ferritin ≥ 100 ng/mL or TSAT $\geq 20\%$.

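### The between-arm test of change in iron dose leaves out never-users and route-changers, so it is not a randomised comparison and its sign can differ from that in all subjects

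*SAP*

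**What the plan says.** Phase 1 SAP 8.5.3(7) tabulates mean monthly iron dose in three categories (oral, intravenous, any route), by interval between scheduled visits and over the whole period to Week 24, together with the change from the screening-period mean. For that change, "The changes should be compared between groups using the Student-t test", and "The mean value of the between-group difference (MT-6548 – darbepoetin), its two-sided 95% confidence interval, t-statistic, and p-value should be provided".

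The item then sets two rules. The first is "If no iron supplement is administered, the dose should be tabulated as 0 mg" (quoted from the final SAP; the Phase 1 SAP has the same sentence). The second removes anyone whose iron route changed on treatment, and adds that "subjects who had never received an iron supplement during the treatment period should be excluded from the tabulation". The removal is written for the item as a whole. The any-route category is not exempted, and no other population is named for the test. Final SAP 8.5.2(7) repeats all of this to Week 52, and final SAP 8.7.1 repeats it for the re-tabulation of Phase 1 data. Phase 1 SAP 4.12 adds that "the dose of iron supplements will not be calculated if iron supplements are used as needed".

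Protocol 8.5.2 has iron given from screening through treatment to hold serum ferritin or TSAT above a threshold, and "Investigators/subinvestigators will determine iron supplement dosage and administration route". Protocol 10.1.3(7) defines the endpoint without any exclusion: "Mean weekly dosage will be calculated for each scheduled study visit from the first day of the treatment period". Protocol 13.1 places efficacy analysis in the FAS, and Protocol 13.3.2(3) plans only descriptive statistics for the other endpoints. Both SAPs nevertheless state that nothing has changed from the protocol.

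**The concern.** Whether a subject receives iron on treatment, and by which route, is decided after allocation by investigators who know the arm, in response to iron indices that the study drug may affect. Restricting the comparison to subjects who used iron and kept one route therefore selects on events that can depend on treatment. The retained subsets are not protected by randomisation, and a t-test on them does not estimate the effect of assignment on iron dose.

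The outcome is a change from screening, which makes the selection act directly on the result. A subject on iron at screening who receives none from the first day of treatment has the largest fall that subject could have. That subject is a never-user for the treatment period and is dropped with the whole fall. A subject who changes route is dropped with whatever change in dose came with it, even from the any-route table, where route has no bearing on the total.

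At stake is how the table is read. A between-arm estimate with a confidence interval and p-value will be taken as randomised evidence on whether MT-6548 alters the amount of iron needed.

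**Working it through.** **The plan's own figures.** The documents give no proportion of iron users, no iron dose, no SD and no power for this endpoint. The only power statement (above 95% with 150 per arm) concerns the primary endpoint and has no bearing here. Everything below on iron use is assumed.

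**Common assumptions.** 150 subjects per arm (SAP 2.5); 60 per arm on 1,000 mg/month at screening and 90 on none. *Stop* means on iron at screening and none from the first day of treatment. *Start* means none at screening and 1,000 mg/month on treatment.

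**Formulae.** Change = treatment-period dose minus screening dose, in mg/month. The all-subjects mean is the sum of changes / 150. The SAP-set mean is the sum of changes among subjects with some treatment-period iron and no route change, divided by their number. Differences are MT-6548 minus darbepoetin.

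**A. Never-user rule.** 40 vs 10 stop, 5 vs 15 start, continuing users change by +200 vs 0.
- All, MT-6548: (40 × −1,000 + 20 × 200 + 5 × 1,000) / 150 = −31,000 / 150 = −206.7
- All, darbepoetin: (10 × −1,000 + 50 × 0 + 15 × 1,000) / 150 = 5,000 / 150 = +33.3
- All, difference: **−240**
- SAP set, MT-6548: (20 × 200 + 5 × 1,000) / 25 = +360.0
- SAP set, darbepoetin: (50 × 0 + 15 × 1,000) / 65 = +230.8
- SAP set, difference: **+129**

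**B. Route rule.** 2 vs 20 move from oral 1,000 to intravenous 3,000 mg/month; other users change by +100 vs 0.
- All: (58 × 100 + 2 × 2,000) / 150 = +65.3 against (20 × 2,000) / 150 = +266.7; difference **−201**
- SAP set (58 vs 40 subjects): +100 against 0; difference **+100**

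**C. Milder never-user case.** 20 vs 10 stop, 10 start in each arm, continuing users change by +100 vs 0.
- All: (−20,000 + 4,000 + 10,000) / 150 = −40 against (−10,000 + 10,000) / 150 = 0; difference **−40**
- SAP set: 14,000 / 50 = +280.0 against 10,000 / 60 = +166.7; difference **+113**

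**Range.** As in C, with 10 starters per arm and 10 stoppers on darbepoetin, varying the MT-6548 stoppers and the change in continuing MT-6548 users:

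| MT-6548 stoppers | Change in continuing users | All subjects | SAP set |
|---|---|---|---|
| 10 | 0 | 0 | 0 |
| 10 | +100 | +33.3 | +83.3 |
| 15 | 0 | −33.3 | +15.2 |
| 15 | +200 | +26.7 | +178.8 |
| 40 | 0 | −200.0 | +166.7 |

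With equal stopping the sign does not reverse, although the size can still differ. Unequal stopping does not always reverse it either (15 stoppers, +200).

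**Sampling variation.** In 3,000 simulated trials per case, with an assumed within-user SD of 400 mg/month, the all-subjects and SAP-set differences had opposite signs in 92% (A), 90% (B) and 84% (C).

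**The case against.** The best defence is that item (7) does not stand alone. Item (8) compares the proportion receiving oral, intravenous or any-route iron, with exact interval and Fisher p-value, and counts never-users. Item (10) compares ferritin, TSAT and hepcidin between arms. A subject who stops iron after even one on-treatment dose stays in item (7), barring a route change, at 0 mg thereafter. This stands: a reader might infer that evidence of lower need through non-use disappears from the report, and it does not. What is still missing is a dose comparison that includes everyone, and the doses of route-changers.

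Three further inferences are tempting and unsupported.

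- *That the 0 mg rule contradicts the exclusion.* Dose is computed per interval between visits, while the exclusion concerns subjects with no iron across the whole treatment period. The 0 mg rule can sensibly cover iron-free intervals in someone treated at other times. The exclusion and its effect remain on that reading.
- *That route-changers are those with the greatest need.* The protocol leaves route to the investigator and names allergy and adverse reactions as grounds for omitting iron; intolerance could equally prompt a switch. The rule also removes changes from intravenous to oral.
- *That on-treatment dose levels alone prove a reversal.* Suppose 30% of MT-6548 subjects average 2,500 mg/month, 50% of darbepoetin subjects average 2,000, and both arms average 800 over all subjects at screening. The all-subjects difference in change is (750 − 800) − (1,000 − 800) = −250. The SAP-set difference is −400 or +100, depending on which subjects held the screening dose. The test is on change, so levels do not settle its sign.

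It is also fair that this is one of 14 other endpoints, which Phase 1 SAP 8.5.4.7 treats as exploratory and does not adjust for multiplicity.

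**Conclusion.** The point holds. As written, the t-test in Phase 1 SAP 8.5.3(7) and final SAP 8.5.2(7) compares subsets chosen by post-randomisation events, and its p-value should not be read as a randomised comparison of iron requirement. That follows from the text and needs no assumption.

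The size does rest on assumptions. In the worked cases the difference moves from −240 to +129, −201 to +100 and −40 to +113 mg/month. Reversal requires the arms to differ in stopping, starting or switching route. A reader might infer that the trial's iron result is reversed, or that the rule favours one drug; the documents show neither, only that the sign can differ.

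The test and the exclusion also depart from the protocol without being declared. The primary non-inferiority conclusion is unaffected, so this is a should-fix on an exploratory table.

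**What to change.** In Phase 1 SAP 8.5.3(7) and final SAP 8.5.2(7):

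- Make the between-arm comparison of change in monthly iron dose on all FAS subjects, with 0 mg wherever no iron was given.
- Keep route-changers in the any-route table, and in the oral and intravenous tables with each route's own dose.
- Treat as-needed iron, whose dose is not calculated, as missing rather than 0 mg, and report the number of subjects affected by arm.
- Report medians beside means because of the many zeros. If most subjects do not change dose the median may be zero in both arms, so it supplements the mean.
- Keep the users-only table as description, without a test.

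In final SAP 8.7.1, keep the Phase 1 method, because that section checks the effect of a data change like for like, and add the all-FAS analysis beside it. List the between-arm test and the exclusion as changes from the protocol. If the new analysis is added after data lock, give the reason and distinguish its results from the original plan, as Protocol 13.4 requires.

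The cost is SAP wording and re-run tables from data already collected.

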8.5.4 Statistical issues

8.5.4.1 Adjustment for covariates

In the analysis of efficacy, in order to consider the effect of the measurement value of the first day of the treatment period on the change of each measurement in the group comparison, the analysis using the MMRM model (with compound symmetry [CS] for a covariance matrix within subject variance) should be conducted using the measurement value of the first day of the treatment period as a covariate in the general analysis including the analysis

of the primary endpoint. A sensitivity analysis of the primary endpoint should be similarly conducted using ANCOVA with the measurement value of the first day of the treatment period as a covariate. In addition, the group comparison of Hb increase rate should be similarly conducted using ANCOVA with the measured value of the first day of the treatment period as a covariate.

8.5.4.2 Use of the “Subpopulation for efficacy evaluation” of patients

The primary analysis for the primary endpoint should also be performed for the PPS to examine the robustness of the results.

8.5.4.3 Handling of dropout or missing data

Provided in “7. Data handling”.

8.5.4.4 Interim analysis and data monitoring

This statistical analysis plan regulates statistical analysis plan of fixed data in the treatment period 1. In the final fixed data, a separate statistical analysis plan should be prepared to perform statistical analysis.

8.5.4.5 Multicenter trial

For FAS, the following analysis should be conducted for each following endpoint for each facilities. Descriptive statistics of Hb values should be calculated at Week 24 of the treatment period (imputed by the LOCF method) for each treatment group.

Descriptive statistics of mean dose of the study drug should be calculated for the Week 20 to Week 24 of the treatment period in the treatment group.

No analysis will be performed for patient cohorts.

8.5.4.6 Subgroup analyses

The following analyses should be conducted for subpopulations based on the stratification factor for each endpoint in the Table below (Table 8.5.4.6) in the FAS. Unless otherwise specified, no analysis will be performed for patient cohorts.

On the Hb value at Week 24 of the treatment period, LSMean, standard error, and 2-sided 95% CI should be calculated for each treatment group using the MMRM model (with compound symmetry [CS] for a covariance matrix within subject variance). The point estimate, its standard errors, 2-sided 95% CI, and p-value of the between-group difference (MT-6548 – darbepoetin) of LSMean should be calculated.

Descriptive statistics of mean dose of the study drug should be calculated for the Week 20 to Week 24 of the treatment period in the treatment group.

With respect to the responder rate at Week 24 of the treatment period (proportion of subjects with increased Hb level by ≥ 1.0 g/dL from the first day of the treatment period), the number of responders, proportion, and 95% CI (Clopper-Pearson [Exact] method) for the proportion should be provided for each treatment group. The estimate, its 95% CI (exact method), and p-value (Fisher's exact test) for between-group difference (MT-6548 – darbepoetin) should be calculated. Only the Correction and Conversion (Hb value < 11.0 g/dL) cohorts should be analyzed.

With respect to the achievement rate of target Hb at Week 24 of the treatment period, the number, rate and 95% CI (Clopper-Pearson [Exact]) method for the rate of subjects with Hb values within the target range (11.0 g/dL to < 13.0 g/dL) should be provided for each treatment group. The estimate, its 95% CI (exact method), and p-value (Fisher's exact test) for group difference (MT-6548 – darbepoetin) should be calculated.

Table 8.5.4.6 Subgroup analyses in efficacy

Endpoints	Stratification factor	Stratified category
1. Hb values at Week 24 of the treatment period	Sex	Male, Female
2. Study drug average dosage at Week 20 to Week 24 of the treatment period	Age at time of consent (years)	<65, ≥65
		<75, ≥75
3. Responder rates at Week 24 of the treatment period	Body weight (kg) on the first day of the treatment period	<60, ≥60
4. Target Hb achievement rate at Week 24 of the treatment period	Body mass index (kg/m ²) on the first day of the treatment period	<25, ≥25
	Underlying cause of CKD	Diabetes, hypertension, autoimmune/glomerulonephritis/vasculitis, interstitial nephritis/pyelonephritis, cystic/hereditary/congenital disease, neoplasm/tumor
	Duration of nephrogenic anemia (years)	<1, 1 to <5, ≥5
	Complication	hypertension, diabetes, dyslipidemia
	Hb value (g/dL) on the first day of the treatment period	<9, 9 to <11, ≥11
	eGFR on the first day of the treatment period (mL/min/1.73 m ²)	<15, 15 to <30, 30 to <60, ≥60
	Liver function test (U/L) on the first day of the treatment period	AST and ALT both below the upper limit of normal, either above the upper limit of normal and both ≤2 times the upper limit of normal, either > 2 times the upper limit of normal
	CRP (mg/dL) on the first day of the treatment period	<0.31, ≥0.31
	Serum ferritin (ng/dL) on the first day of the treatment period	Divide the number of subjects into three categories based on the tertile
	TSAT (%) on the first day of the treatment period	Divide the number of subjects into three categories based on the tertile
	Smoking status	3 categories: never smoked, ex-smoker, current smoker
	Administration of oral iron on the first day of the treatment period	Yes or No
	Treatment with oral iron supplement at Week 24 of	Yes or No

	the treatment period	
	Iron-containing phosphate binders on the first day of the treatment period	Yes or No
	Iron-containing phosphate binders at Week 24 of the treatment period	Yes or No
	Previous ESA formulation (Conversion cohort only)	Epoetin Alfa or epoetin beta, darbepoetin alfa, epoetin beta pegol, other
	Epoetin alfa or epoetin beta weekly dose (IU) (Conversion cohort only)	Divide the number of subjects into three categories based on the tertile
	Darbepoetin alfa weekly dose (µg) (Conversion cohort only)	Divide the number of subjects into three categories based on the tertile
	Epoetin beta pegol dose (µg) (Conversion cohort only)	Divide the number of subjects into three categories based on the tertile
	CYP2B6 inducer combination *	Yes or No

* List of CYP2B6 inducers obtained from The Metabolism and Transport Drug Interaction Database (DIDB ®).

